### **6.4. Blinding**

This is a double-blind, sponsor-unblinded study.

#### **6.4.1. Blinding of Participants**

Participants and their parent(s)/legal guardian will be blinded to their assigned study intervention.

#### **6.4.2. Blinding of Site Personnel**

Investigators and other site staff will be blinded to participants' assigned study intervention.

Participants will be assigned to receive study intervention according to the assigned treatment group from the randomization scheme. Investigators will remain blinded to each participant's assigned study intervention throughout the course of the study.

In the event of a Quality Assurance audit, the auditor(s) will be allowed access to unblinded study intervention records at the site(s) to verify that randomization/dispensing has been done accurately.

#### **6.4.3. Blinding of the Sponsor**

As this is a sponsor -open study, the sponsor may conduct unblinded reviews of the data during the course of the study for the purpose of safety assessment, facilitating dose finding decisions, facilitating PK/PD modeling, and/or supporting clinical development.

#### **6.4.4. Sensitive Clinical Data**

Sensitive clinical data are data collected in this study that have the potential to unblind a participant's treatment assignment. Access to sensitive clinical data will be restricted to authorized individuals until the study has been unblinded. The following data variables are considered sensitive clinical data: Assigned treatment group (Active versus placebo); PK parameters.

#### **6.4.5. Breaking the Blind**

The IRT will be programmed with blind-breaking instructions. In case of an emergency, the investigator has the sole responsibility for determining if unblinding of a participant's treatment assignment is warranted. Participant safety must always be the first consideration in making such a determination. If the investigator decides that unblinding is warranted, the investigator should make every effort to contact the study medical monitor prior to unblinding a participant's treatment assignment unless this could delay further management of the participant. If a participant's treatment assignment is unblinded, the sponsor must be notified within 24 hours after breaking the blind. The date and reason that the blind was broken must be recorded in the source documentation and CRF.

The study-specific IRT reference manual and IPM will provide the contact information and further details on the use of the IRT system.

### **6.5. Study Intervention Compliance**

When the individual dose is prepared on site, the preparation of the dose will be confirmed by a second qualified member of the study site staff.

When participants are dosed at the site as an outpatient, they will receive study intervention directly from the parent(s)/legal guardian under medical supervision.

The date and time of each dose administered will be recorded in the eDiary ([Appendix 10D](#) in [Section 10.10.4](#)). The dose of study intervention and study participant identification will be confirmed at the time of dosing by a member of the study site staff other than the person administering the study intervention. Study site personnel will examine each participant's mouth to ensure that the study intervention was ingested, if applicable.

When participant's parent(s)/legal guardians administer study intervention(s) at home, compliance with study intervention will be assessed at the next consecutive visit. Compliance will be assessed by direct questioning and counting returned bottles with initially dispensed study intervention at the end of the study and documented in the source documents and eDiary. Deviation(s) from the prescribed dosage regimen should be recorded in the CRF.

A record of the number of study intervention doses dispensed to and administered to each participant must be maintained and reconciled with study intervention and compliance records. Intervention start and stop dates, including dates for intervention delays will also be recorded in the CRF.

If the study participant is hospitalized at the time of enrolment and it is identified that they (he/she) could not attend the Day █ and/or Day █ visits if discharged, the investigator may at their (his/her) discretion, if local regulations allow and [CCI](#) █ services are not available, keep the participant in the hospital for convenience to ensure Day █ and/or Day █ assessments can be conducted in compliance with protocol requirements.

Participants may be replaced at Sponsor discretion as described in [Section 4.1](#) and [Section 9.5](#).

Any deviation from protocol-specified dosing (eg, missed single dose or partial dose) should be recorded as a protocol deviation and the investigator or designee is to counsel the participant/guardian and ensure steps are taken to improve compliance.

## **6.6. Dose Modification**

Dose modification within a cohort is not allowed. For further details on dose selection for each cohort, see [Section 4.1](#).

## **6.7. Continued Access to Study Intervention After the End of the Study**

No study intervention will be provided to participants at the end of their study participation. It is expected that participants will be treated as required with standard-of-care treatments, as advised by their usual care physician.

## **6.8. Treatment of Overdose**

For this study, any single dose of sisunatovir greater than the prescribed daily dose of study intervention will be considered an overdose. There is no specific treatment for an overdose.

In the event of an overdose, the investigator/treating physician should:

1. Contact the study medical monitor within 24 hours.
2. Closely monitor the participant for any AEs/SAEs and laboratory abnormalities as medically appropriate and follow-up until resolution, stabilization, the event is otherwise explained, or the participant is lost to follow-up (as defined in Section 7.3).
3. Document the quantity of the excess dose as well as the duration of the overdose in the CRF.
4. Overdose is reportable to Pfizer Safety only when associated with an SAE.
5. Obtain a blood sample for PK analysis within 24 hours from the day of the last overdose.

Decisions regarding dose interruptions will be made by the investigator in consultation with the study medical monitor as needed based on the clinical evaluation of the participant.

Parent(s)/legal guardian should store the study intervention out of reach of children to avoid any situations that could result in overdosing.

#### 6.9. Prior and Concomitant Therapy

- Use of following antiviral will be recorded in the CRF
  - Prior treatment with Nirsevimab

#### Prohibited Prior Treatments

- Prohibited concomitant medications that may result in DDI (Section 10.8)
- Receipt of corticosteroids equivalent to prednisone  $\geq 2$  mg/kg daily for at least 14 consecutive days within 30 days prior to study start.
- Antivirals within 10 days of screening.
- Treatment with ribavirin (oral or inhaled) within 30 days of screening.
- Treatment with biologics (eg, infliximab, ustekinumab), immunomodulators (eg, methotrexate, 6MP, azathioprine) or cancer chemotherapy within 90 days prior to study start.
- Has taken within 5 half-lives plus 14 days before dosing any drug that could impact the PK of the investigational product, including any prescription medications, OTC medications, herbal remedies or dietary supplements containing St. John's Wort or the consumption of [REDACTED] as these are known to be [REDACTED]

- Administration of proton pump inhibitors must have ended 5 days prior to randomization.
- Administration of H2 blockers must have ended at least 12 hours prior to randomization.
- Previous administration with an investigational product (drug or vaccine) within 30 days (or as determined by the local requirement) or 5 half-lives preceding the first dose of study intervention used in this study (whichever is longer).

#### Prohibited During the [REDACTED] Day Study Drug Administration

- Prohibited concomitant medications that may result in DDI (Section 10.8).
- Biologics (eg, infliximab, ustekinumab), immunomodulators (eg, methotrexate, 6MP, azathioprine) or cancer chemotherapy.
- Antivirals for respiratory tract infection.
- Requires any drug or food that could impact the PK of the investigational product, including any prescription medications, OTC medications, herbal remedies or dietary supplements containing St. John's Wort or the consumption of [REDACTED] CCI [REDACTED] products as these are known to be CCI [REDACTED]
- Any administration of proton pump inhibitors and H2 blockers is prohibited. The use of antacids (such as calcium carbonate or magnesium hydroxide) is allowed with staggered dosing (ie, not within 3 hours before or after study drug administration).

## 7. DISCONTINUATION OF STUDY INTERVENTION AND PARTICIPANT DISCONTINUATION/WITHDRAWAL

### 7.1. Discontinuation of Study Intervention

It may be necessary for a participant to permanently discontinue study intervention. Reasons for permanent discontinuation of study intervention include the following:

- Death
- Occurrence of an AE or any other condition posing a risk to a participant or jeopardizing a safe continuation of the study treatment for the respective participant (as judged by the investigator, and/or the national coordinators, and/or the Medical Monitor and the study sponsor)
- Missing any dose prior to the [REDACTED] CCI draw

- Requirement of prohibited concomitant medications during the study (See [Appendix 8](#) in Section 10.8)
- Study terminated by sponsor

Discontinuation of study intervention does not represent withdrawal from the study. If study intervention is permanently discontinued, the participant should remain in the study to be evaluated for follow-up visits. Unplanned visits following permanent discontinuation of study intervention, if needed will be conducted per Day ~~CC1~~ visit in the [SoA](#). See the [SoA](#) for data to be collected at the time of discontinuation of study intervention and follow-up for any further evaluations that need to be completed.

In the event of discontinuation of study intervention, it must be documented on the appropriate CRF/in the medical records whether the participant is discontinuing further receipt of study intervention or also from study procedures, further study follow-up, and/or future collection of additional information.

#### 7.1.1. Potential Cases of Acute Kidney Injury

See [Appendix 6](#) in Section 10.6 for kidney safety monitoring guidelines and discontinuation criteria.

Participants exposed to IMP demonstrating transient or sustained increase in Screat (with decrease in Screat-based eGFR) require expedited evaluation to differentiate AKI from DICI. DICI is defined as transporter-mediated effect related to altered renal tubular creatinine handling without histological injury.

##### **Differentiating Acute Kidney Injury from DICI:**

AKI may be due to one or more types of injury, including DIKI. Differentiation of DIKI from other causes of AKI and from DICI, may require clinical, radiographic, histopathologic, and laboratory assessments, as well as nephrology consultation.

Screat increase is defined as:

##### **Infants and Children $\geq 28$ days old and $< 12$ years old:**

- (i) Screat increase  $\geq 0.3$  mg/dL ( $\geq 26.5$   $\mu$ mol/L) within 48 hours OR
- (ii) Screat increase  $\geq 1.5$  times baseline known or suspected to have occurred within the prior 7 days

##### **Neonates $< 28$ days old:**

- (i) Screat increase  $\geq 1.5$  to 1.9 times from baseline (previous lowest value) known or suspected to have occurred within the prior 7 days OR
- (ii) Screat increase  $\geq 0.3$  mg/dL ( $\geq 26.5$   $\mu$ mol/L) within 48 hours.

- Based on the assessments performed, suspected AKI (including DIKI) may be differentiated from DICI as follows in [Table 5](#).

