#### 4.1.1. Dose Finding and Stopping Rules

The Sponsor will make the final decision of doses for the cohorts, including recommendation to repeat a dose or opening enrollment of the subsequent cohort. The E-DMC approval of the Sponsor's recommendation to repeat a dose or opening enrollment of the subsequent cohort will be independently assessed for each of the different age groups and will be based on the safety/tolerability and concentration data.

Repeat dosing at the assessed dose level or progression to the higher dose level will not occur if:

- Mean  $C_{max}$  **CCI** ng/mL and Mean  $AUC_{24}$  **CCI** ng•h/mL, within an age band (**CCI**)

Dosing or enrollment interruption will occur if any of the following is observed:

- Death of a participant during participation in the study receiving study intervention (sisunatovir) and assessed as possibly, probably, or definitely related to study intervention (sisunatovir) by the Investigator(s) and/or Sponsor.
- Two or more SAEs in the same SOC in the study receiving study intervention (sisunatovir) assessed as possibly, probably, or definitely related to study intervention (sisunatovir) by the Investigator(s) and/or Sponsor.
- Severe nonserious AEs, considered as, at least, possibly related to study intervention (sisunatovir), in 2 participants (receiving sisunatovir), independent of within or not within the same organ class, indicating dose limiting intolerance.
- Two or more participants receiving study intervention (sisunatovir) experience the same or a similar AE that is assessed as severe in intensity and in the opinion of the E-DMC and/or Sponsor, represent an unacceptable risk to participants enrolled in the trial.
- If two or more participants receiving study intervention (sisunatovir) develop similar clinically significant laboratory, or vital sign abnormalities, in the same organ class, indicating dose limiting intolerance.

If any of the above criteria are fulfilled, restart of dosing will only be possible if agreed by the E-DMC. Should a clear non-IMP cause for any of the above be identified, the study may continue.

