#### 8.3.4. Clinical Safety Laboratory Assessments

See [Appendix 2](#) for the list of clinical safety laboratory tests to be performed and the [SoA](#) for the timing and frequency. All protocol required- laboratory assessments, as defined in [Appendix 2](#), must be conducted in accordance with the laboratory manual and the [SoA](#). Unscheduled clinical laboratory measurements may be obtained at any time during the study to assess any perceived safety issues.

Laboratory safety parameters will be graded according to DAIDS Table for Grading the Severity of Adult and Pediatric Adverse Events [\[11\]](#).

The investigator must review the laboratory report, document this review, and record any clinically significant changes occurring during the study in the AE section of the CRF. Clinically significant abnormal laboratory test findings are those that are not associated with the underlying disease, unless judged by the investigator to be more severe than expected for the participant's condition.

All laboratory tests with values considered clinically significant and abnormal during participation in the study or within [CCI](#) [REDACTED] should be repeated until the values return to normal or baseline or are no longer considered clinically significant by the investigator or study medical monitor.

If such values do not return to normal/baseline within a period of time judged reasonable by the investigator, the etiology should be identified, and the sponsor notified.

See [Appendix 5](#) in Section 10.5 for suggested actions and follow-up assessments in the event of potential DILI.

See [Appendix 6](#) in Section 10.6 for instructions for laboratory testing to monitor kidney function and reporting laboratory test abnormalities.

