[Table 6](#) provides the blood volume allowed to be drawn in participants (neonates, infants, and children) up to 60 months of age. All safety labs should be done locally only. Every effort should be made to limit the amount of blood collected from each participant over the duration of the study. The maximum amount of blood collected from each participant over the duration of the study, including any extra assessments that may be required, will not exceed the volumes in [Table 6](#). Repeat or unscheduled samples are allowed based on clinical judgment for participant safety or for technical issues with the samples. The total blood volumes for the different age groups take into account the estimated blood volume for participants at the fifth percentile for weight in each of the cohorts [\[12,13\]](#) and total blood volumes. Per these criteria, 1% of total blood volume is allowed to be drawn within 24 hours

and 3% of total blood volume is allowed to be drawn within 4 weeks. These volumes are shown in Table 7 for all cohorts.

A 1-day old child is the youngest subject to be enrolled in the study. It is calculated that a 1-day old child may weigh 2.5 kg and has 90 mL of blood/kg. Therefore, a 1-day old child likely has a total blood volume of 225 mL. Per the criteria of 1% of total blood volume allowed to be drawn within 24 hours and 3% of total blood volume allowed to be drawn within 4 weeks, this equals an allowance of 2.25 mL of blood in 24 hours and 6.75 mL of blood in 4 weeks for a 2.5 kg child.

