#### 10.6.3. Adverse Event Grading for Kidney Safety Laboratory Abnormalities

The KDIGO produces guidelines regarding kidney diseases prevention or management. For example, in the KDIGO guideline regarding chronic kidney disease, GFR category recommendations are available for reference.

AE grading for decline in kidney function will be according to the modified KDIGO criteria for neonates [18] and KDIGO criteria for infants and children  $\geq 28$  days old to  $< 12$  years old [19] as indicated below.

| Criteria used for Staging | Study Population | Stage 1  | Stage 2                                    | Stage 3  |
|---------------------------|------------------|--|--|--|
| Modified KDIGO Criteria   | All Ages         | (i) $\geq 0.3$ mg/dL Screat increase within 48 hours OR
(ii) $\geq 1.5$ to $1.9$ times Screat increase from baseline (previous lowest value) within prior 7 days) | 2.0-2.9 fold Screat increase from baseline | $\geq 3$ fold Screat increase from baseline OR
Increase in Screat to $\geq 4.0$ mg/dL ( $\geq 353.6$ mmol/l) OR
RRT initiation |

| KDIGO albuminuria (A) criteria    | A1                           | A2                                      | A3                             |
|-----------------------------------|------------------------------|---|--------------------------------|
| Albumin-to-creatinine ratio (ACR) | <30 mg/g
OR
<3 mg/mmol | 30 to 300 mg/g
OR
3 to 30 mg/mmol | >300 mg/g
OR
>30 mg/mmol |

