## Monitoring and Discontinuation Criteria for All Cohorts

| Potential Criteria       | Recommendations  |
|--------------------------|--|
| Monitoring Criteria      | 
Neonates < 28 days old:
(i) Screat increase <math>\geq 0.3</math> mg/dL (<math>\geq 26.5</math> <math>\mu</math>mol/L) within 48 hours OR
(ii) Screat increase <math>\geq 1.5</math> to 1.9 times from baseline (previous lowest value) known or suspected to have occurred within the prior 7 days
 
Infants and children <math>\geq 28</math> days old and < 12 years old:
(i) Screat increase <math>\geq 0.3</math> mg/dL (<math>\geq 26.5</math> <math>\mu</math>mol/L) within 48 hours OR
(ii) Screat increase <math>\geq 1.5</math> times baseline known or suspected to have occurred within the prior 7 days
 |
| Discontinuation Criteria | 

Two sequential increases in serum creatinine that confirm the above changes over the screening or baseline value as indicated in the monitoring criteria.

Note: If the serum creatinine increases may be caused by an identifiable and reversible reason (eg, concomitant medication), then an additional retest may be allowed after discussion with the medical monitor. After retest, a decision for the subject to continue in the study will be made after discussion with the medical monitor.

   |

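### The relative creatinine trigger for participants under 28 days stops at 1.9-fold, so a rise of 2-fold or more counts only if it is also at least 0.3 mg/dL within 48 h

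*Protocol*

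**What the plan says.** Protocol Section 7.1.1 defines a serum creatinine increase separately by age.

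- **Under 28 days:** either at least 1.5 "to 1.9 times from baseline (previous lowest value) known or suspected to have occurred within the prior 7 days", or at least 0.3 mg/dL (26.5 µmol/L) within 48 hours.
- **28 days and older:** the same absolute limb, or at least 1.5 "times baseline known or suspected to have occurred within the prior 7 days", with no upper limit.

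Section 7.1.1 sends the reader to Appendix 6 (Section 10.6) "for kidney safety monitoring guidelines and discontinuation criteria". The table there, Monitoring and Discontinuation Criteria for All Cohorts, repeats both age-specific definitions as the monitoring criteria. It then sets the discontinuation criterion as "Two sequential increases in serum creatinine that confirm the above changes over the screening or baseline value".

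Section 10.6.3 grades kidney adverse events for all ages. Stage 1 uses the 1.5 to 1.9 band, Stage 2 is a "2.0-2.9 fold Screat increase from baseline", and Stage 3 starts at 3-fold.

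On who is affected, Section 8.3.4 states: "A 1-day old child is the youngest subject to be enrolled in the study".

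**The concern.** A range that separates Stage 1 from Stage 2 makes sense in a grading table. As a trigger it excludes the more serious rises. Under 28 days, a 1.8-fold rise meets the relative limb, while a 2-fold or 3-fold rise (Stage 2 or 3) does not and must qualify through the absolute limb. The open-ended line for older participants sits in the same cell of the Section 10.6 table, so a site could take the difference as deliberate.

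The discontinuation rule is defined only by reference to the monitoring criteria, so it has the same hole. At stake is the numeric kidney threshold for the youngest participants. The completed pediatric study described in Section 4.3 began at 1 month of age and gives no data under 28 days.

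**Working it through.** **1. The plan's own figure.** At 88.4 µmol/L per mg/dL, 0.3 × 88.4 = 26.52 µmol/L, which agrees with the stated 26.5.

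**2. The rule taken literally.** Let b be baseline creatinine (mg/dL) and f the fold-rise, so the absolute rise is b(f − 1). Under 28 days the criterion is met if

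- 1.5 ≤ f ≤ 1.9 within 7 days, or
- b(f − 1) ≥ 0.3 within 48 h.

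For f ≥ 2 only the second limb remains. Strictly, the gap opens just above 1.9.

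**3. Inputs.** Baselines come from Table 9 (Section 10.6.2), rows day 1 to 3 weeks. The 4-week row is 28 days, falls under the open-ended rule, and is left out.

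**4. Missed at any speed.** A doubling adds b, so it is below 0.3 mg/dL whenever b < 0.30. The absolute limb is reached at f = 1 + 0.3/b, and the missed values run from 2b up to, but not including, b + 0.3.

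| Age | Centile | b | f that reaches +0.3 | Values missed (mg/dL) |
|---|---|---|---|---|
| Day 5 | 2.5th | 0.28 | 2.07 | 0.56 to <0.58 |
| Day 6 | 2.5th | 0.27 | 2.11 | 0.54 to <0.57 |
| Day 7 | 2.5th | 0.26 | 2.15 | 0.52 to <0.56 |
| 2 weeks | 2.5th | 0.24 | 2.25 | 0.48 to <0.54 |
| 2 weeks | 10th | 0.27 | 2.11 | 0.54 to <0.57 |
| 3 weeks | 2.5th | 0.21 | 2.43 | 0.42 to <0.51 |
| 3 weeks | 10th | 0.25 | 2.20 | 0.50 to <0.55 |

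On days 1 to 4 even the 2.5th centiles (0.42, 0.36, 0.33, 0.31) reach +0.3 at 1.71-, 1.83-, 1.91- and 1.97-fold, so no doubling within 48 h is missed there.

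Worked pair from b = 0.25: 0.45/0.25 = 1.8, inside the band, so the criterion is met. For 0.50, f = 2.0 is outside the band and the rise is 0.25 < 0.3, so neither limb is met.

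**5. Missed by timing.** Assume a steady rise over 5 days (120 h). The share falling in any 48 h is 48/120 = 0.4.

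- *Doubling:* the 48 h rise is 0.4b, below 0.3 when b < 0.75. At the Table 9 medians for days 1 to 7, 2 weeks and 3 weeks (0.62, 0.53, 0.48, 0.44, 0.42, 0.41, 0.38, 0.35, 0.32) it is 0.248, 0.212, 0.192, 0.176, 0.168, 0.164, 0.152, 0.140 and 0.128. The doubled value meets neither limb at any of them.
- *Tripling:* the 48 h rise is 0.4 × 2b = 0.8b, below 0.3 when b < 0.375. At the day 1 to 7 medians it is 0.496 down to 0.304, so it qualifies. At 2 and 3 weeks it is 0.280 and 0.256, so a Stage 3 rise is missed.

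These results describe the end value. A rise passing through 1.5- to 1.9-fold is caught if a sample happens to be drawn in that band.

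**6. Cap removed.** With f ≥ 1.5 within 7 days, every rise of 2-fold or more within 7 days qualifies at any baseline.

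**7. Schedule.** Table 7 (Section 8.3.4) shows three chemistry draws, one of them at baseline. Stopping needs two sequential increases, so on scheduled draws the rule can be met only at the last one. Any earlier effect depends on unscheduled retests.

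**The case against.** The strongest reply is that this is a drafting slip that would rarely change what happens to a child.

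- **Intent.** The sign before 1.5 suggests a floor, and Section 10.6.3 treats 2-fold and 3-fold rises as higher stages of the same event. That is probably what was meant. But in Section 10.6.3 the same expression has to be a closed band, because Stage 2 begins at 2.0, and the line for older participants has no cap.
- **Firmness of the rule.** The Section 10.6 table presents its content as potential criteria and recommendations, and allows a further retest after discussion with the medical monitor if a reversible cause is suspected. It is therefore not an automatic stop. It is still the kidney discontinuation criterion to which Section 7.1.1 refers.
- **Little time to act.** Dosing lasts 5 or 6 days and scheduled draws are few. This stands, and it limits the benefit of any correction.
- **Sampling in the timing example.** A steady 5-day doubling sampled at 96 h is at 1 + 96/120 = 1.8-fold and would qualify. This also stands. The laboratory days are redacted, so how often it would help is unknown.
- **Narrow ranges.** The values missed at any speed span only 0.02 to 0.09 mg/dL, at low centiles. True.
- **Other safeguards.** Clinically significant values "should be repeated until the values return to normal or baseline or are no longer considered clinically significant by the investigator" or medical monitor (Section 8.3.4). Section 7.1 allows judgment-based stopping. Section 7.1.1 lets albuminuria or low urine volume raise suspicion whatever the creatinine, and treats unexplained confirmed declines as potential drug-induced injury. Section 4.1 provides external committee review by age group. Section 4.1.1 interrupts dosing or enrollment when two or more treated participants "develop similar clinically significant laboratory, or vital sign abnormalities" in the same organ class, indicating dose-limiting intolerance. The amendment history adds, as context, that little drug is excreted in urine.

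These safeguards reduce the harm; none of them corrects the threshold. The expedited evaluation in Section 7.1.1 does not fully stand apart either, because it is triggered by a creatinine increase that the same section defines with the cap.

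**Conclusion.** The point holds. Under 28 days, the kidney monitoring and discontinuation criteria as written are weaker for larger rises than for smaller ones. Where the rise is fast, the gap is confined to baselines below 0.30 mg/dL: the 2.5th centile at days 5 to 7, and the 2.5th and 10th centiles at 2 and 3 weeks. Where it is slow, the gap can reach every Table 9 median under 28 days for a doubling, and the 2- and 3-week medians for a tripling.

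This rests on a literal reading of the two passages and, for slow rises, on an assumed steady 5-day course. The figures illustrate the gap and do not estimate a rate of missed events: the documents give no event rate, and the number of participants under 28 days is redacted. Practical harm is likely to be limited, since a sensible investigator would probably act on a doubling. It is nonetheless an error in a safety threshold and should be corrected.

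**What to change.** Delete the upper bound of 1.9 in the under-28-days definition in Section 7.1.1 and in the neonatal line of the Section 10.6 monitoring table. Both relative limbs then read as at least 1.5 times baseline, keeping the previous-lowest-value definition of baseline and the 7-day window. Leave the Stage 1 band in Section 10.6.3 unchanged, where a closed range is right.

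The cost is a wording change in two places, with no new scheduled samples or tests and possibly a few more retests. One loose end remains: the creatinine row of Table 5 still requires a rise of at least 0.3 mg/dL in both columns. A rise from 0.25 to 0.50 mg/dL would then enter the work-up but fit neither column on that row.
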